
9.4.2.2 End of Study

A subject is considered to have completed the study when the 90 Day Visit is completed. For those subjects who fail to complete a 90 Day Visit, subjects are considered to have exited the study at the time of withdrawal of consent or death occurring prior to the 90-day visit window, or, for those considered lost to follow-up, at 150 days from randomization, when the 90-day visit plus 60 days window closes.

Form 17: End of Study should be completed in the WebDCU™ system for every subject once the subject has exited the study.

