1 STUDY FLOWCHARTS

1.1 Graphical Study Design

1.2 Schedule of Activities and Assessments

Contact Schedule and Measurements

Measurements	Screening	Baseline/ Randomization	Phone F/U Day 7 +/-2	Phone F/U Day 30 ^o	Phone or In- Person F/U Day 90 +/- 14 [†]	Event Visit***	End of Study
Screen Failure Log	x						
Eligibility Form		x					
Consent (including optional study)		x					
Randomization Form		x					
Enrollment/ Demographics		x					
ABCD ² Score		x					
Modified Rankin Scale (mRS)					x	x	
NIH Stroke Scale		x			x	x	x
Medical History		x					
Prior Medications		x					
Index TIA/Minor Stroke Symptoms		x					
Vital Signs		x					
Blood Sample (optional)		x* ²					
Head CT/MRI Scan		x*			x*	x*	
ECG		x*			x*	x*	
Carotid Imaging		x* ¹			x* ¹	x*	
Stroke-Free Questionnaire: QVSFS			x	(x)	x	x	
Morisky Questionnaire			x	(x)	x	x	
Concomitant Medications Form			x		x	x	
SAE/Clinical Outcome Reporting			x		x	x	
Study Drug Compliance				(x)			x
Final Diagnosis		x					
End of Study Form							x
Protocol Violation	x	x	x		x	x	x

*Part of standard evaluation; cost not covered by study.

** As needed (visit can occur more than once).

*** Event Visits for MI can be completed by telephone.

† Preferably as soon as possible after the completion of 90 days.

¹ Encouraged as part of best practices but not required for study entry or at 90 days. If performed, record results on CRF.

² Blood sample obtained with subject's consent for optional ancillary study

Ø No study data collected.

Note: Certain follow-up assessments, such as the mRS and QVSFS, by telemedicine are acceptable.

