7.5 Treatment Discontinuation

The study drug should be continued whenever possible. If temporary interruption of study medication is required for surgery or other therapy, the subject's regimen will be resumed when it is considered safe by the subject's neurologist or primary care physician. Study medications will be restarted after carotid endarterectomy. If a clear indication for anticoagulation is revealed during the 90-day study period (atrial fibrillation, for example), study medications will be stopped and anticoagulation will be initiated.

If the study drug is stopped, it should be determined if the discontinuation can be made temporarily; permanent study drug discontinuation should be a last resort. Pregnancy will lead to definitive treatment discontinuation in all cases. In any case, all randomized subjects should remain in the study and followed per the protocol to 90 days from randomization, or to death, whichever comes first, even if the subject discontinues the POINT study drug regimen, unless the subject withdraws consent to participate in the trial.

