8.5 SAEs/Clinical Outcomes

8.5.1 SAEs/Clinical Outcomes into the Study Database

All SAEs/Clinical Outcomes occurring until participation in study has ended are recorded on the online SAE/Clinical Outcome Reporting Form (CRF 19) through the WebDCU™. The Site PI or Study Coordinator is responsible for entering any and all SAEs into the database and updating the information (e.g., date of resolution, action taken), as needed, in a timely manner. Given the vast amount of data on AEs associated with clopidogrel, only SAEs/Clinical Outcomes will be recorded; data entry must take place within **5 days (within 24 hours for sites in the UK)** of discovery of the event.

The Hub PI for NETT sites and site PI for others are responsible for the monitoring and follow-up of all SAEs/Clinical Outcomes until resolution (or end of study for that subject) and appropriate documentation in the subject research record. In addition to performing protocol-specified follow-up,

the participating PI must review all previously reported ongoing SAEs/Clinical Outcomes to evaluate the current status.

Upon completion of the study by the subject, premature withdrawal from the study by the subject, or subject's death, all information regarding each SAEs/Clinical Outcome must be completed, if not done so earlier.

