9.4.3 Event Visit

An Outcome Event Visit should be conducted if a subject experiences an ischemic stroke, TIA, or myocardial infarction. Outcome Event Visits should be conducted in person unless the subject experiences a myocardial infarction or refuses to come for an in-person visit. CRF completion for the visit will be guided by whether the visit was conducted by phone or in person. Event visits are conducted as needed, and can be done more than once for the same subject.

A listing of data collected during event visits is included in Section 1.2. SAEs/Clinical Outcomes, concomitant medications, mRS, NIHSS, QVSFS, and Morisky Questionnaire will be recorded. Head imaging with CT or MRI will be strongly encouraged to document stroke and after any suspected TIA. ECG and cardiac enzyme will be required to document myocardial infarction. Appropriate laboratory testing will be required for documentation of systemic hemorrhage or other systemic complications. Autopsy will be encouraged when cause of death is unclear. If study medications are discontinued due to an outcome or SAE, they should be restarted as soon as felt to be safe by the treating physician. Event visits may occur on the same day as the 90-day visit since it is expected that clinical outcome events may often be identified at the 90 day visit. Each subject will continue to be followed through 90 days post randomization.

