10.2 Statistical Analyses

10.2.1 Primary Outcomes

The primary analysis will be intention to treat, with inclusion and treatment group defined per the randomization assignment. Missing values will remain missing and subjects will be censored at their last follow-up assessment (end of study or last visit prior to loss to follow-up). Kaplan-Meier estimates of the cumulative risk of an event will be reported for the maximum 90-day follow-up, and the log-rank test will be used to evaluate the statistical significance of the treatment effect. The Type I error for the primary analysis will consider two-sided $\alpha=0.05$ significant.

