### 12.1.3. Primary Efficacy Analysis (ITT)

The primary efficacy null hypothesis of the equality of survival curves is tested with the log-rank test. The overall Type I error for the primary analysis will consider two-sided alpha=0.05 significant.

The primary analysis will be intention to treat, with inclusion and treatment group defined at the randomization assignment. Missing values will remain missing and patients will be censored at their last follow-up assessment; based on projected loss rates, it is expected that only 5 subjects will be lost at 7 days and 70 subjects lost at 90 days, so the problem is relatively minor. Kaplan-Meier estimates of the cumulative risk of an event during maximum 90-day follow-up will be reported, with HRs and 95% CI calculated using Cox proportional hazards methods (to provide an estimate of treatment effect) and the log-rank test to evaluate the treatment effect. This approach is being taken to maximize the time dependent information in the trial while still acknowledging the ease of interpretation of risks. For the Cox proportional hazards method, the Efron method will be used when there are ties since this method closely approximates the exact method, but requires less computing resources.

The primary outcome is composite of ischemic stroke, MI, or ischemic vascular death occurring up to 90 days. However, the 90 day visit may occur within +-14 days of the target visit. For patients with an event, the time to event will be the days from randomization to the first adjudicated primary outcome event (if it occurred before 90 days). Events occurring after 90 days (e.g. day 91) will not be counted in the primary analysis. Patients for whom there was no event and whose follow-up visit occurred after day 90 will be censored at exactly 90 days. For patients without a 90 day visit, the censoring date will be determined by the last collected QVSFS (censoring time will be the actual days from randomization). The Kaplan Meier curves will use the actual days up to day 90. For this figure, the "# at risk" will be reported at baseline, 7 days, and 90 days.

Likewise, the ITT analysis will be repeated for the primary and secondary efficacy and safety outcomes.

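### The final visit may take place from day 76 and ends the patient's participation, so up to 14 of the 90 risk days can go unobserved

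*Protocol*

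**What the plan says.** The schedule in Protocol 1.2 places the last contact at day 90 ± 14, with a footnote on timing: "Preferably as soon as possible after the completion of 90 days". SAP 12.1.3 repeats the window: "However, the 90 day visit may occur within +-14 days of the target visit".

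Protocol 9.4.2.2 ties the end of the study to that visit: "A subject is considered to have completed the study when the 90 Day Visit is completed". Protocol 8.5.1 ties event capture to participation: "All SAEs/Clinical Outcomes occurring until participation in study has ended are recorded".

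Other sections state the aim of full follow-up. Protocol 7.5 says "all randomized subjects should remain in the study and followed per the protocol to 90 days from randomization", or until death, and Protocol 9.4.3 says "Each subject will continue to be followed through 90 days post randomization".

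SAP 12.1.3 has a specific censoring rule for an event-free patient whose visit falls after day 90 (censored at day 90) and another for a patient with no 90-day visit (the last stroke-free questionnaire). An event-free visit on days 76–89 has no rule of its own. Only the general rule, given also in Protocol 10.2.1, reaches it: "Missing values will remain missing and subjects will be censored at their last follow-up assessment". The same approach covers safety: "Likewise, the ITT analysis will be repeated for the primary and secondary efficacy and safety outcomes".

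SAP 13.2 lists proportions for specific events. Deaths are counted to 90 (± 14) days, and major, minor and intracranial hemorrhages to 90 days.

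**The concern.** Both primary outcomes are defined over 90 days, yet a site can complete a patient on day 76 without learning the status at day 90 and without a protocol deviation. Protocol 7.5 and 9.4.3 show what was intended, but they assign no contact, form or check to a patient who came early.

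The contrast with Protocol 8.5.3 and 9.4.2.1 is odd. For a patient who is hard to reach, the site must try until day 150 to establish 90-day status. For a cooperative patient seen two weeks early, nothing further is required.

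What is at stake is late events in both arms, a little power, and the clarity of the 90-day summaries. In SAP 13.2 the deaths and the hemorrhages run over different horizons, and a crude hemorrhage proportion makes no allowance for days not observed.

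**Working it through.** **Inputs.** Window day 90 ± 14 (Protocol 1.2, SAP 12.1.3). Hazard ratio 0.75, 530 events, 90% power, placebo proportion 15.24% at 90 days, 5.0% inflation, N = 4,142 rounded up to 4,150 (SAP 5.1). Boundaries 3.710, 2.511 and 1.993 at 177, 353 and 530 events (SAP Table 2). In the emergency-department cohort, 73% of composite events fell in the first month (Protocol 2.6). Expected rates of 2% for major hemorrhage and 3% for death (SAP 13.2).

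**The plan's own figures.** The treated proportion is 1 − (1 − 0.1524)^0.75 = 0.1166, so the mean proportion is 0.1345. Then 530 / 0.1345 × 1.05 ≈ 4,137, against the stated 4,142. The expected final Z is √(530/4) × ln(1/0.75) = 3.311. Trivariate normal integration over the three boundaries gives power 0.9086, against the stated 90%. The design is reproduced.

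**Unobserved days.** Earliest visit: 90 − 14 = day 76. Days 77–90 are 14 days, and 14/90 = 15.6% of the risk period.

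**Share of events in those days.** Spreading the 27% of events after day 30 evenly over 60 days (an assumption): 0.27 × 14/60 = 6.3%, or 33.4 of 530.

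**Events missed and power.** The documents do not say how many patients are seen early, so two assumptions are shown, with an upper bound for each.

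- A: a share f is seen on day 76. Missed = 530 × 0.063 × f.
- B: visits are spread evenly over days 76–104. Half are early, on average 7 days short, so the mean shortfall is 3.5 days. Missed = 530 × 0.27 × 3.5/60.

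| Assumption | Events missed | Power |
|---|---|---|
| None seen early | 0 | 0.909 |
| A, f = 5% | 1.7 | 0.908 |
| A, f = 25% | 8.3 | 0.904 |
| B | 8.3 | 0.904 |
| B, constant hazard from 15.24% | 19.1 | 0.898 |
| Everyone seen on day 76 | 33.4 | 0.890 |

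**SAP 13.2 summaries, constant hazard.** The proportion by day d is 1 − (1 − p)^(d/90).

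- Major hemorrhage, p = 2%: 1.69% by day 76. Averaged over assumption B, the crude proportion reads about 1.92%.
- Death, p = 3%: 1 − 0.97^(76/90) = 2.54% if counted to day 76, and 1 − 0.97^(104/90) = 3.46% if counted to day 104.

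**The case against.** The strongest reply is that follow-up to day 90 is stated more than once and the schedule footnote steers visits past day 90. On that reading, 9.4.2.2 concerns completion status only and does not switch off event capture. The Manual of Procedures, which is not available here, may also contain a later check. The effect is slight in any case: power stays above 0.90 under both A and B. The constant-hazard row contradicts the cohort timing, and assumption B ignores the footnote. The re-estimation to 5,840 used a placebo rate gathered under the same window. SAP 13.2 is descriptive, and the main safety analyses are censored. A change at this stage needs Executive Committee approval and, as appropriate, ethics review at up to 350 sites. Study tablets last only to day 90, so barring earlier visits could delay the hand-off to onward therapy.

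Most of the argument on size stands. The loss is small, part of it may already be absorbed in the re-estimated sample size, and the constant-hazard rows are bounds and not expectations. The 2.54% and 3.46% death figures are likewise the two ends of the stated window.

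The argument on the text does not close the gap. Sections 7.5 and 9.4.3 state an aim, 9.4.2.2 lets a site finish without meeting it, and neither protocol nor SAP supplies a step that reconciles them. The hand-off argument has little force, because the footnote already asks for visits after day 90 and the telephone option leaves visit timing unchanged. The approval burden is real but is an administrative cost.

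**Conclusion.** The concern holds. The final visit is allowed from day 76, it completes the study, and a visit after day 90 is only a preference.

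The effect is a loss of late events, not of validity. Provided visit timing is unrelated to risk, censoring at the last assessment keeps the primary and major-hemorrhage time-to-event analyses sound. Assumptions A and B cost at most about 8 of 530 events and half a point of power; the constant-hazard bound for B costs 19 events and about one point. These figures rest on an even spread of events after the first month and on assumed shares of early attenders.

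Two side effects point the same way. Protocol 9.4.2 makes clopidogrel the default prescription at the final visit, so a placebo patient seen early could start it within the 90 days. Protocol 9.4.4 requires 71 tablets over days 2–90, while a patient seen on day 76 can have taken at most 75, so the 80% threshold becomes 71/75 ≈ 95%.

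The mismatch of horizons in SAP 13.2 is a separate and purely descriptive point. The change is worth making because it costs little, not because the trial's conclusion depends on it.

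**What to change.** - **Window.** In Protocol 1.2 and SAP 12.1.3, set the final visit at day 90 to day 104. Alternatively, keep ± 14 days and, after any visit before day 90, require a brief call on or after day 90 that completes Form 14 and the Form 19 review before Form 17 is signed off.
- **Completion.** In Protocol 9.4.2.2, define completion as outcome status known through day 90.
- **Censoring.** In SAP 12.1.3, say outright that an event-free patient last assessed before day 90 is censored on that date.
- **SAP 13.2.** Count deaths to day 90, so that deaths and hemorrhages share one horizon, and give the hemorrhage summaries as Kaplan-Meier 90-day estimates.

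The cost is a few words in each section plus the usual approvals, and either slightly less scheduling freedom or one short call per early attender. The means exist already: Protocol 9.4.2 accepts a telephone final visit, and 9.4.2.1 accepts Form 14 or Form 19 information from the patient, a caregiver or an alternate contact for the primary analysis. The day 90–104 window also removes the two side effects on open-label clopidogrel and tablet counts; the call alone does not.

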9.4.3 Event Visit

An Outcome Event Visit should be conducted if a subject experiences an ischemic stroke, TIA, or myocardial infarction. Outcome Event Visits should be conducted in person unless the subject experiences a myocardial infarction or refuses to come for an in-person visit. CRF completion for the visit will be guided by whether the visit was conducted by phone or in person. Event visits are conducted as needed, and can be done more than once for the same subject.

A listing of data collected during event visits is included in Section 1.2. SAEs/Clinical Outcomes, concomitant medications, mRS, NIHSS, QVSFS, and Morisky Questionnaire will be recorded. Head imaging with CT or MRI will be strongly encouraged to document stroke and after any suspected TIA. ECG and cardiac enzyme will be required to document myocardial infarction. Appropriate laboratory testing will be required for documentation of systemic hemorrhage or other systemic complications. Autopsy will be encouraged when cause of death is unclear. If study medications are discontinued due to an outcome or SAE, they should be restarted as soon as felt to be safe by the treating physician. Event visits may occur on the same day as the 90-day visit since it is expected that clinical outcome events may often be identified at the 90 day visit. Each subject will continue to be followed through 90 days post randomization.

9.4.4 Adherence to Treatment

Subject adherence with the study drug (clopidogrel and placebo) and aspirin will be assessed by administering the Morisky medication adherence questionnaire at the 7 day telephone call, the 90 day visit, and at the event visit. The 4-question Morisky scale is a simple, commonly used, validated adherence measure (*Morisky, DE; Green, LW; Levine, DM. 1986, Medical Care, 24, 1. p.67-74*). This will serve as the primary measure of adherence. A participant is considered compliant with study medication if he/she reported at least medium compliance on the study adherence questionnaire. The investigator will be responsible for monitoring subject adherence. A subject will be counseled on the importance of complying with the study medication.

In addition, for clopidogrel, compliance with the study drug will be documented at the 90-day visit. Those subjects taking more than 80% of tablets on days 2-90 (71 or more tablets) will be considered adherent as assessed by pill count and subject/care-giver report. NOTE: Since the loading dose is observed by the study investigator or other member of the study team (see Manual of Procedures section 11.4, Study Procedures) and recorded on CRF 7, subjects will be considered to be in compliance with the loading dose. Therefore, a subject is adherent if he/she has taken at least 79 tablets (8 at loading dose + 71 on days 2-90).

The sites identified for the study have reported adherence rates of about 95% in prior stroke trials. However, if there are systematic problems with adherence at a particular site, the NETT and CRC will know this rapidly and will contact the site to identify possible solutions.

Concomitant medications will also be recorded at follow-up visits.

10 STATISTICAL CONSIDERATIONS

10.1 Statistical Analysis Plans

This section is an overview of the statistical considerations. Complete details can be found in the Statistical Analysis Plan (SAP). It provides the general specifications for the analysis of the data to be collected and presented in the Clinical Study Report. A final SAP will be issued by the SDMC prior to database lock and before code breaking. The SAP will define all “pre-specified, planned analyses.”

10.1.1 Randomization Scheme

Randomization will be implemented centrally via the WebDCU™ system. The randomization scheme will ensure treatment is balanced within site and overall. The study will include both TIA and minor ischemic stroke, with the latter accounting for no more than 50% of enrollment.

10.1.2 Sample Size Estimates

Primary Null Hypothesis

In patients with high-risk TIA or minor ischemic stroke treated with aspirin 50-325 mg/day, there is no difference in the event-free survival at the 90-day follow-up in those treated with clopidogrel (600 mg loading dose then 75 mg/day) compared to placebo when subjects are randomized within 12 hours of time last known free from new ischemic symptoms. The primary outcome is a composite consisting of ischemic stroke, myocardial infarction, or ischemic vascular death; the primary safety outcome is major hemorrhage.

The original maximum sample size to detect a relative risk reduction (RRR) of 23% is 4,150 subjects. As stipulated in the Statistical Analysis Plan, following the first interim analysis, the maximum sample size has been re-estimated to be 5,840 subjects. The original sample size estimation is based on 90% power and a two-sided alpha of 0.05, 12% crossovers, and 2% losses to follow-up. The RRR of 23% translates to a hazard ratio of 0.75 assuming the proportion of subjects with events in the placebo group to be 15%, and inflation to account for two interim analyses for efficacy at equal intervals using O’Brien and Fleming stopping boundaries.

10.1.3 Secondary Outcomes

A number of other secondary outcomes will be evaluated separately, including risk of ischemic stroke, intracranial hemorrhage, and major hemorrhage, and the composite of the primary outcome and major hemorrhage. The influence of index event type (TIA vs. minor stroke), sex, and race/ethnicity will be evaluated in subgroup analyses.

10.2 Statistical Analyses

10.2.1 Primary Outcomes

The primary analysis will be intention to treat, with inclusion and treatment group defined per the randomization assignment. Missing values will remain missing and subjects will be censored at their last follow-up assessment (end of study or last visit prior to loss to follow-up). Kaplan-Meier estimates of the cumulative risk of an event will be reported for the maximum 90-day follow-up, and the log-rank test will be used to evaluate the statistical significance of the treatment effect. The Type I error for the primary analysis will consider two-sided $\alpha=0.05$ significant.

10.2.2 Secondary Outcome Events

The analysis strategy outlined for the primary outcome will be used for most of the secondary analyses. Each secondary outcome event at the two-sided α of 0.05 will be tested, recognizing the dangers of inflating the Type I error probabilities. These tests will be viewed as exploratory hypotheses that may or may not support the results of the primary analysis.

